through all imputed data sets before estimates and standard errors are combined using the pool()
function in the "mice" package.

391 The variable names may differ in the actual data set.

392

390

376 377

378

380 381

382

383

384

385

386

For each risk ratio estimate, we will also compute an indicative risk difference (RD; see the tables in section 8). This will be done by taking the difference between a point estimate of the control risk and the product of that control risk and the estimated risk ratio. The indicative RD will be presented by with a 95% confidence interval.

397

398 9.1.1 Sensitivity analyses

The estimator proposed for the case that 5% or more wards do fully not adhere to their randomized treatment involves accounting for an intercurrent event (incomplete adherence to NOST due to, for example, late start or cessation) by estimating the log risk ratio of being randomized to and adhering to NOST as $\beta_X + \beta_A$, where a_i , the variable for coefficient β_A , is a continuous variable in [0, 1] with $a_i = 0$ modelling no adherence to NOST and $a_i = 1$ modelling full adherence to NOST. Because this analysis requires a modelling assumption, we will perform sensitivity analyses for each analysis that uses the model proposed.

406

In the first sensitivity analysis, we will estimate marginal risk ratios using a restricted estimation sample that will exclude wards that did not adhere to the treatment to which they were assigned (i.e., we will exclude wards randomized to NOST which did not fully implement NOST, and exclude wards randomized to control that partially or fully implemented NOST). The restricted estimation sample will be analyzed using the following model:

412 413

414

$$n_i \sim B(N_i, p_i)$$
 where $\log p_i = \beta_0 + \beta_X x_i$

415 where the log risk ratio of fully adhering to NOST is estimated by β_X .

416 417 In the second sensitivity analysis, we will model adherence using a factor variable, with k + 1 levels 418 that model degree of adherence to NOST. We will estimate marginal risk ratios (RRs) using binomial 419 regression as follows:

- 420 421 422
- $n_i \sim B(N_i, p_i)$ where $\log p_i = \beta_0 + \beta_X x_i + \beta_{A1} a_{i1} + \beta_{A2} a_{i2} + \dots + \beta_{Ak} a_{ik}$

423 where $\{a_{i1}, a_{i2}, ..., a_{ik}\}$ are binary variables that indicate the non-reference levels of the factor 424 variable that models adherence (these variables will be created automatically in software), and 425 $\{\beta_{A1}, \beta_{A2}, ..., \beta_{Ak}\}$ are log risk ratios for the non-reference levels. We will define the reference 426 (i.e., base) level to be no adherence to NOST and estimate the effect of being randomized and 427 adhering to NOST as $\beta_X + \beta_{A1}$, where β_{A1} is the log risk ratio for the level of the factor variable 428 corresponding to full adherence to NOST.

429

Having obtained the three estimates of the effect of being randomized and adhering to NOST (i.e., one from the analysis specified in section 9.1 and one for each of the two sensitivity analyses), we will assess the sensitivity of our estimates to the assumptions underpinning the three models using seemingly unrelated estimation¹ (SUE) as follows. Let { $\gamma_1, \gamma_2, \gamma_3$ } denote the three estimates on the log risk ratio scale. Sensitivity will be assessed using a two-sided Wald test of the hypothesis $\gamma_1 = \gamma_2 = \gamma_3$. We will report the result of this test and interpret the p-value according to the following table:

P-value	Estimates γ_1 , γ_2 , and γ_3 all statistically exclude no effect	Interpretation
<0.05	Yes, same directions	 The magnitude of the effect of being randomized and adhering to NOST is sensitive to modelling assumptions. The direction of the effect of being randomized and adhering to NOST is not sensitive to modelling assumptions.
<0.05	Yes, different directions	 One or both sensitivity analyses disagreed with the main estimator of the effect of being randomized and adhering to NOST. The effect of the intervention is unclear.
<0.05	No	 One or both sensitivity analyses disagreed with the main estimator of the effect of being randomized and adhering to NOST. The effect of the intervention is unclear.
≥0.05	Yes, same directions	 The magnitude of the effect of being randomized and adhering to NOST is not sensitive to modelling assumptions. The direction of the effect of being randomized and adhering to NOST is not sensitive to modelling assumptions.
≥0.05	Yes, different directions	This condition is nonsensical: it should not be possible for the estimates to indicate different directions of effect and for the test that they are equal to suggest they are.
≥0.05	No	 The magnitude of the effect of being randomized and adhering to NOST is not sensitive to modelling assumptions. The direction of the effect of being randomized and adhering to NOST is not sensitive to modelling assumptions.

¹ Note that, in Stata, use of SUE requires that clustering within hospital be specified as an option to **suest** rather than **binreg** for all models, and that the variance-covariance matrix of the estimates (VCE) be computed using the observed, rather than the expected, information matrix (i.e., using the **vce (oim)** option of **binreg**).

9.2 Mean Difference Estimation 438

439 If fewer than 5% of wards do not adhere to their randomized treatment, we will estimate marginal 440 differences in means using linear regression with cluster-robust standard errors, with hospital as the cluster variable: 441

442 443

449

452

453

459

461 462

463

466

444 where for the bed days per inpatient stay outcome, y_i is bed days per inpatient stay for the *i*th hospital 445 446 ward, β_0 estimates the mean for controls, x_i indicates if the *i*th hospital ward was randomized to NOST, β_x estimates the effect of being randomized to NOST as a marginal mean difference, and σ is 447 448 the residual standard deviation.

 $y_i \sim N(\beta_0 + \beta_X x_i, \sigma)$

450 If 5% or more wards do fully not adhere to their randomized treatment, we will estimate marginal 451 differences in means using the model:

 $y_i \sim N(\beta_0 + \beta_X x_i + \beta_A a_i, \sigma)$

454 455 where $0 \le a_i \le 1$ models the degree of adherence by the *i*th hospital ward to NOST (see section 7.6 and the definition of a_i in section 9.1) and β_A estimates the effect of full adherence to NOST. The 456 457 marginal mean difference of being randomized to and adhering to NOST is estimated by $\beta_X + \beta_A$. We will use the same strategy for handling possible nonconvergence as described in section 9.1. 458

460 Estimation can be performed using Stata as follows:

```
regress bed i.treat c.adh, vce(cluster hospital)
```

464 where data are arranged with one ward per row, bed is a variable containing bed days per inpatient 465 stay, and the other variables are defined as in section 9.1.

467 Estimation can be performed using R as follows:

468

469

model = glm(bed ~ treat + adh, data = df, family = gaussian(link = "identity") coeftest(df, vcov. = vcovCL(model, cluster = hospital)

471 472

470

473 9.2.1 Sensitivity analysis

474 We will perform sensitivity analyses similar to those for risk ratios (see section 9.1.1).

10 Estimands 475

476 This section presents all estimands in terms of the objective, a statement of the estimand in plain 477 language, the target population (i.e., who or what the estimate can be applied to), the analysis set 478 (i.e., what subset, if any, of the full analysis set will be used to perform the analysis), the outcome 479 variable, strategies for handling ICEs and missing data, the effect measure that will be estimated, and 480 the estimator used to perform the analysis.

481 **10.1 Primary Outcome Estimand**

Objective To assess the effect of NOST with respect to compliance with hand hygiene recommendations.

Estimand The risk of compliance with hand hygiene recommendations, measured at one year, by employees who perform patient-related work in Norwegian hospitals if NOST was introduced and

SAP version: 1.1

adhered to versus if NOST was not introduced and not adhered to.			
Target population Employees	Analysis set All		
Outcome Variable Compliance with hand hygiene recommendations			
ICE Strategy See sections 7.6, 9.1, and 9.1.1	Missing Data Strategy See section 7.5		
Effect Measure(s) RR and indicative RD	Estimator Binomial regression with cluster-		
	robust standard errors		

483 **10.2 Secondary Outcome Estimands**

484 **10.2.1 Outbreaks (VESUV)**

Objective To assess the effect of NOST with respe	ct to outbreaks.	
Estimand The risk of outbreak, measured over one year, in Norwegian hospital wards if NOST was		
introduced and adhered to versus if NOST was not introduced and not adhered to.		
Target population Hospital wards	Analysis set All	
Outcome Variable Outbreaks (VESUV)		
ICE Strategy See sections 7.6, 9.1, and 9.1.1	Missing Data Strategy See section 7.5	
Effect Measure(s) RR and indicative RD	Estimator Binomial regression with cluster-	
	robust standard errors	

485 **10.2.2 Inpatient Infection (VESUV)**

Objective To assess the effect of NOST with respe	ct to inpatient infection (using data from VESUV).		
Estimand The risk of inpatient infection defined as part of an outbreak, measured over one year, in			
Norwegian hospital wards if NOST was introduced and adhered to versus if NOST was not			
introduced and not adhered to.			
Target population Inpatients	Analysis set Wards with reported outbreak		
Outcome Variable Inpatient infections (VESUV)			
ICE Strategy See sections 7.6, 9.1, and 9.1.1	Missing Data Strategy See section 7.5		
Effect Measure(s) RR and indicative RD	Estimator Binomial regression with cluster-		
	robust standard errors		

486 **10.2.3 Employee Infection (VESUV)**

Objective To assess the effect of NOST with respe	ect to employee infection.	
Estimand The risk of employee infection as defined part of an outbreak, measured over one year,		
in Norwegian hospital wards if NOST was introduced and adhered to versus if NOST was not		
introduced and not adhered to.		
Target population Employees	Analysis set Wards with reported outbreak	
Outcome Variable Employee infections (VESUV)		
ICE Strategy See sections 7.6, 9.1, and 9.1.1	Missing Data Strategy See section 7.5	
Effect Measure(s) RR and indicative RD	Estimator Binomial regression with cluster-	

487 10.2.4 Inpatient Infection (NOIS)

Objective To assess the effect of NOST with respect to inpatient infection (using data from NOIS).		
Estimand The risk of inpatient infection, measured over one year in repeated prevalence studies,		
in Norwegian hospital wards if NOST was introduced and adhered to versus if NOST was not		
introduced and not adhered to.		
Target population Inpatients	Analysis set All	
Outcome Variable Inpatient infection (NOIS)		
ICE Strategy See sections 7.6, 9.1, and 9.1.1	Missing Data Strategy See section 7.5	
Effect Measure(s) RR and indicative RD	Estimator Binomial regression with cluster-	
	robust standard errors	

488 10.2.5 Inpatient Antibiotic Treatment (NOIS)

Objective To assess the effect of NOST with respect to inpatient antibiotic treatment.		
Estimand The risk of inpatient antibiotic treatment, measured over one year in repeated prevalence		
studies, in Norwegian hospital wards if NOST was introduced and adhered to versus if NOST was		
not introduced and not adhered to.		
Target population Inpatients	Analysis set All	
Outcome Variable Inpatient antibiotic treatment (NOIS)		
ICE Strategy See sections 7.6, 9.1, and 9.1.1	Missing Data Strategy See section 7.5	
Effect Measure(s) RR and indicative RD	Estimator Binomial regression with cluster-	
	robust standard errors	

489 **10.2.6** Inpatient Postoperative Site Infection (NOIS-POSI)

Objective To assess the effect of NOST with respect to inpatient treatment for postoperative site infection.

Estimand The risk of postoperative site infection, measured over one year in periods of incidence surveillance of patients undergoing certain surgical procedures, in Norwegian hospital wards if NOST was introduced and adhered to versus if NOST was not introduced and not adhered to.
 Target population Inpatients undergoing surgical procedures monitored in NOIS-POSI groups (included in the NOIS-POSI surveillance)
 Outcome Variable Inpatient postoperative site infection (NOIS-POSI)
 ICE Strategy See sections 7.6, 9.1, and 9.1.1
 Effect Measure(s) RR and indicative RD

robust standard errors

490 10.2.7 Inpatient HAI Diagnosis (NPR)

Objective To assess the effect of NOST with respect to inpatient HAI diagnosis.		
Estimand The risk of inpatient HAI diagnosis, measured over one year, in Norwegian hospital wards		
if NOST was introduced and adhered to versus if NOST was not introduced and not adhered to.		
Target population Inpatients	Analysis set All	
Outcome Variable Inpatient HAI diagnosis (NPR)		
ICE Strategy See sections 7.6, 9.1, and 9.1.1	Missing Data Strategy See section 7.5	
Effect Measure(s) RR and indicative RD	Estimator Binomial regression with cluster-	
	robust standard errors	

491 10.2.8 Bed-days per Inpatient per Stay (NPR)

Objective To assess the effect of NOST with respect to bed-days per inpatient per stay.Estimand The mean number of bed-days per inpatient per stay, measured over one year, in
Norwegian hospital wards if NOST was introduced and adhered to versus if NOST was not
introduced and not adhered to.Target population InpatientsAnalysis set AllOutcome Variable Bed-days per stay (NPR)
ICE Strategy See sections 7.6, 9.2, and 9.2.1Missing Data Strategy See section 7.5
Estimator Linear regression with cluster-robust
standard errors

492 **11 Reporting Conventions**

In general, percentages in the table of baseline characteristics will be rounded to whole numbers, andsummaries of continuous variables will be presented to one decimal place.

495

496 Statistical estimates will be presented as points with two-sided 95% confidence intervals and *p*-values.

497 Point estimates and confidence intervals will be reported to 2 decimal places, and *p*-values will be 498 reported to three decimal places or as p < 0.001.

499 **12** Quality Assurance of Statistical Programming

- 500 The statistical code will be written and tested on fictitious data. Testing will include producing all 501 results, tables, and figures as they will appear in the final manuscript prior to analyzing the trial data.
- 502
- Analysis code and data will be versioned using an appropriate system to be chosen by the analyst andmay be published alongside the trial results.

13 Summary of Changes to the Protocol and/or SAP

506 This section is to be completed to document and justify any changes to a published version of this SAP.

507 **14 Acknowledgements**

The template used to produce this SAP was derived with permission from a template developed by
 the Michigan Institute for Clinical and Health Research (MICHR; grant UL1TR002240), which was based
 in turn on version CCTU/TPLV2 of the template produced by Cambridge University Hospitals Clinical

511 Trials Unit.

512 **15 References**

- 5131.van Buuren, S. and K. Groothuis-Oudshoorn, mice: Multivariate Imputation by Chained514Equations in R. Journal of Statistical Software, 2011. 45(3): p. 1 67.
- 515 2. International Council for Hamonisation, *E9(R1) Statistical Principles for Clinical Trials:* 516 *Addendum: Estimands and Sensitivity Analysis in Clinical Trials, May 2021*. 2021.
- 517

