Control	Not implementing NOST				
Primary outcome	Compliance with hand hygiene recommendations by hospital employees who do patient-related work, measured at one year after randomization.				
Design	Cluster-randomized parallel two-arm superiority trial.				
Blinding	Trial participants and other personnel cannot be blinded to treatment allocation. The trial statistician will be blinded to treatment allocation.				
Treatment allocation	Hospital wards will be randomized 1:1. Randomization will be stratified by hospital to ensure approximately equal allocation of wards within hospital.				

99

101

The following table shows the structure of data registered in NOST: 104

1	n	5
т	υ	J

Plac	Place Observation of hand hygiene			2	Person	
Hospital	Ward	Section number	Observation number	Indication	Compliance	Profession
1	5	1	1	А	1	Nurse
			2	В	1	
			3	D	0	
1	4	2	4	В	1	Physician
2	2	3	5	А	0	Nurse
			6	В	1	
			7	С	0	
			8	С	0	
			9	E	1	
1	5	4	10	A	1	Nurse
			11	E	1	assistant

- 107 Description of the variables:
- Hospital: a unique ID-number for each hospital. The data will also include information about
 the actual health trust and health region
- Ward: a unique ID-number for each ward within the actual hospital. The wards will be allocated to intervention and control arms
- Section number: a unique running number for a section of observations where the observer has followed a person and registered all hand hygiene indications happening within a specific setting or task. A section will most often include several observations where the person has or should have performed hand hygiene.
- Observation number: a unique running number for an observation where hand hygiene was
 or should have been performed
- Indication: A code for why hand hygiene was advised, based on the guidelines by the World
 Health Organization
- Compliance: A code displaying whether the person performed hand hygiene or not (1 or 0)
 when the indication arose
- Profession: The health profession of the observed person. Other personal information is not registered. Only one person is observed within a section number, but the same persons may be observed in several sections
- 125

126 4.2 General Study Populations and Inclusion-Exclusion Criteria

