127 There are three general study populations (see above and the study protocol). This SAP introduces a 128 third population not specified in the protocol, hospital ward. This was introduced because one of the 129 secondary outcomes (outbreaks) cannot be measured at the level of employee or inpatient but can 130 be measured at the level of ward.

- 131
- We will exclude hospitals and their associated randomized wards from all analyses if the hospital after randomization decides not to implement or to terminate the execution of NOST, and the decision is communicated to the Norwegian Institute of Public Health.
- 135

136 **4.3 Treatment Allocation**

Stratified randomization will be used to allocate wards to 1:1 intervention and control arms. Randomization will be stratified by hospital. Randomization will be performed using a computer-based system and the investigators will not be able to manipulate treatment allocation. The approach is outlined in the protocol.

141 **4.4 Blinding/Masking**

142 It is not possible to blind trial participants or observers to treatment allocation. While much of the 143 outcome data will be obtained from registries (e.g., to which events are notified), the people who 144 report data may not be blinded to treatment allocation. However, the trial statistician who will analyze 145 the data will be blinded to treatment allocation.

146

147 When all data have been collected, a member of the research group will apply a blind to the treatment 148 allocation variable, so that the statistician will not know which arms correspond to the intervention 149 and control treatments. The analysis of the primary outcome will be performed blinded. Before 150 unblinding, we will publish a short document on Zenodo describing how the result for the primary 151 outcome was interpreted by the project team. The blind will then be removed and the secondary

analyses will be performed unblinded.

153 **5 Outcomes**

154 **5.1 Primary outcome**

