wards randomized and not excluded (see exclusion criteria, above). In practical terms, the data set
will have one ward per row and there will be 9 outcome variables (columns), plus covariates.
Outcomes will be analyzed in the arms to which the wards were randomized.

182 **7.3 Covariates and Subgroups**

183 Because randomization is stratified by hospital, we originally planned to adjust for hospital as a fixed 184 effect in all analyses. However, the planned adjustment would require estimating one parameter for 185 each hospital (minus the reference hospital), in addition to treatment effect. The large number of parameters that would therefore need to be estimated could lead to imprecision on the effect 186 187 estimates and possibly also estimation problems. Further, the trial is unlikely to include all hospitals 188 in Norway and hence the sample will not exhaust all possible levels of the hospital variable. For these 189 reasons, and the chosen regression model (see section 9), we will account for the likely clustering of 190 outcomes within hospital using cluster-robust standard errors, with hospital as the cluster variable.

191

192 We will obtain data on the following variables to support four subgroup analyses:

- 193
- 194 1. Hospital department (e.g., psychiatry, orthopedics, neurology, ...)
- 195 2. Employee profession (e.g., physician, nurse, ...)
- 196 3. Indications of hand hygiene (e.g., before patient contact, after exposure to body fluid,)
- 197

198 These subgroups are based on the hypothesis that baseline hand hygiene compliance may differ by 199 type of ward or type of profession with different levels of education or work tasks, and compliance 200 may vary depending on the situations in which hand hygiene is recommended. It may be the case that 201 treatment effect is different in these subgroups. (For example, if some ward types already have 202 exceptionally high baseline compliance with hand hygiene recommendations, then only a small 203 beneficial treatment effect is possible for this subgroup. Conversely, if a type of ward or profession 204 has exceptionally low baseline compliance for all or some of the indications then a large beneficial 205 treatment effect may be achievable in this subgroup.

206

207 7.4 Multiple Centers

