We will not combine outcomes by ward or hospital (i.e., we will not define "pseudo-centers"). We will not explore treatment-by-hospital interactions. Between-hospital differences in risk of compliance, for example, will be accounted for using cluster-robust standard errors with hospital as the cluster variable.

212 **7.5 Missing Data**

We will examine the data for spurious values and seek to verify or obtain correct values if data are miscoded (e.g., negative counts, nonintegral values entered for counts, or counts that appear to be unrealistically large). We will report any data processing decisions that need to be made at the time of analysis.

217

218 It is very unlikely that data will be missing for the treatment, hospital, or ward variables, which are219 needed in all analyses.

- 220
- 221 Data may be missing for the primary outcome variable, which is measured by observers. It is unlikely

- that data will be missing for the secondary outcome variables, which will be obtained from registries,
 but data will be missing if hospitals do not provide data to the registries (Norwegian Institute of Public
- 224 Health).
- 225

If wards do not provide outcome data for the primary outcome, we will contact them and ask them to provide the missing data. If more than 5% of wards do not provide primary outcome data, we will use Little's test to assess if the data are unlikely to be missing completely at random (MCAR) but missing at random (MAR). If we assess the data to be MAR, we will use multiple imputation by chained equations (MICE) and perform the prespecified analyses including all wards.

231

The primary outcome comprises counts of observations and counts of those observations that meet the criteria for compliance. We anticipate that both counts will be missing for wards that do not provide outcome data. It will therefore be necessary to impute missing values for these variables in a way that ensures both are valid counts, and that the number of compliances is not greater than the number of observations imputed for a given ward. We will do this as follows.

237

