263 The secondary outcomes depend on registry data. It is possible that some wards or hospitals will either 264 never report data or will intermittently report data. Both possibilities represent missing outcome data 265 problems. We will therefore follow the same general approach as for missing primary outcome data. 266 In the case that secondary outcome data is known to be intermittently reported (i.e., data for some collection periods are available for certain wards, but no data have been reported by the wards for 267 268 other periods), we will use MICE to impute for the collection periods with missing data and then 269 compute the total number of inpatients infected (for example). The imputed outcome is therefore a function of imputed variables (a "passive" variable), which should be handled carefully in the analysis. 270 271 In Stata, it is necessary to use the syntax "mi passive: generate..." or 272 "mi register passive...", prior to "mi estimate:..." to ensure the passive variables are generated correctly in the imputed data sets. In R, passive variables can be handled using the approach
described in section 3.4 of van Buuren and Groothuis-Oudshoorn [1].

275

276 Unless legally or ethically prohibited, we will report any missing data and wards or hospitals that 277 cannot be included in analysis, for example due to withdrawal from the trial.

278 7.6 Intercurrent Events

279 Recall from section 3.2 that the research question is about the effect of implementing and adhering 280 to NOST. We anticipate that some wards may not adhere or fully adhere to the treatment to which 281 they were randomized. For example, a ward may have been randomized to implement and adhere to 282 NOST for the one-year period of the trial, but either did not implement NOST or did not fully adhere. 283 Similarly, a ward may have been randomized to the control arm (i.e., to not implement NOST), but 284 NOST was partially or fully implemented. Because such events would occur after randomization and 285 would change the interpretation of the outcome from that originally intended and hence give a 286 treatment effect estimate that does not have the intended interpretation, non-adherence can be 287 treated as an intercurrent event (ICE) [2].

288

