With respect to the primary outcome, n_i is the number of compliances in the *i*th hospital ward, N_i is the number of observations made in the *i*th hospital ward, β_0 estimates log risk in control, x_i indicates if the *i*th hospital ward was randomized to NOST, β_X estimates the effect of being randomized to NOST as a marginal log risk ratio. The marginal log risk ratio of being randomized to and adhering to NOST is estimated by β_X .

If 5% or more wards do fully not adhere to their randomized treatment, we will estimate marginal risk
 ratios (RRs) using binomial regression as follows:

354 355 356

 $n_i \sim B(N_i, p_i)$ where $\log p_i = \beta_0 + \beta_X x_i + \beta_A a_i$

357 Here, $0 \le a_i \le 1$ models the degree of adherence by the *i*th hospital ward to NOST (see section 7.6) 358 with $\alpha_i = 0$ corresponding to non-adherence and $\alpha_i = 1$ corresponding to full adherence, and β_A 359 estimates the effect of full adherence to NOST. The marginal log risk ratio of being randomized to and adhering to NOST is estimated by $\beta_X + \beta_A$. Note that the x_i and a_i may be highly correlated (almost 360 collinear) because we expect that most wards that implement NOST will also adhere to NOST. For this 361 reason, we will not interpret β_X and β_A separately. We will assume that the statistical software will 362 cope well with the high correlation but will address this issue during analysis in the case of 363 364 nonconvergence.

365

366 Estimation can be performed using Stata as follows (see footnote 1 on page 14):

367 368 binreg compliances i.treat c.adh, n(observations) rr vce(cluster hospital) 369

370 where data are arranged with one ward per row, compliances is a variable containing the numbers

of observations where the employees comply, treat is a treatment indicator where 1 indicates randomization to NOST, adh is a variable containing adherences (which would be omitted if fewer than 5% of wards do not adhere to their randomized treatment), observations is a variable containing the numbers of observations made, and hospital is a factor variable that codes for the hospital to which the wards belong. Treatment effect can then be estimated on the log scale using:

lincom _b[1.treat] + _b[adh]

379 Estimation can be performed using R as follows:

If the analysis is performed in R after imputation (see section 7.5), the script will be run in a loop

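### The SAP removes the blind before the eight secondary outcomes are analysed, gives no reason, and leaves some choices for them to be made after the arms are known

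*SAP*

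**What the plan says.** **Blinding.** The Blinding row of the design table in SAP 4.1 states "The trial statistician will be blinded to treatment allocation", with no limit attached. The opening paragraph of SAP 4.4 says the same of the statistician who does the analysis. The second paragraph of 4.4 sets the order. Allocation is masked once data collection is complete. Then "The analysis of the primary outcome will be performed blinded". The team's interpretation of that result is posted publicly. After that, "The blind will then be removed and the secondary" "analyses will be performed unblinded". No reason is given for stopping there.

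**Data.** SAP 7.2 describes one data set with a row per ward, in which "there will be 9 outcome variables (columns), plus covariates".

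**Choices left to the analysis stage.**
- SAP 7.5, on implausible values: "We will report any data processing decisions that need to be made" once analysis is under way.
- SAP 7.5, on missing registry data: the plan is to "follow the same general approach as for missing primary outcome data", and to impute individual collection periods where reporting was intermittent.
- SAP 9.1, on near-collinearity of arm and adherence: the software is assumed to "cope well with the high correlation but will address this issue during analysis" if the model does not converge. SAP 9.2 adopts the same strategy for length of stay.
- SAP 9.2.1 gives the length-of-stay sensitivity analyses one sentence, pointing to those for risk ratios.

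**Safeguards.** Analyses follow database lock (7.1). Deviations are reported and justified (8.2). Each outcome has an estimand table naming effect measure and estimator (section 10). Code for all results is tested on fictitious data beforehand (section 12).

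**The concern.** The SAP treats analyst blinding as worth having: it masks the allocation variable and commits the team to a public interpretation before the arms are revealed. That protection ends just before the outcomes that answer the protocol's second objective. Whoever settles the open points for infection, antibiotic use and length of stay will know which arm is NOST and will have seen the primary result.

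Decisions about which counts are implausible, whether missing reports are ignorable, or how to rescue a model that fails can all move an estimate. Made with the arms known, they can drift towards the expected direction (fewer infections, shorter stays) without anyone intending it. A sceptical reader of a positive secondary finding could not rule this out from the plan as written.

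**Working it through.** This is a question of sequence, so the check is mainly a reading of the SAP. The plan gives no figure to reproduce apart from the number of outcomes.

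**1. How many outcomes are affected.** SAP 7.2 counts 9 outcome variables, of which 1 is primary: 9 − 1 = 8. The table in SAP 5.2 lists eight: three from VESUV, two from NOIS, one from NOIS-POSI and two from NPR. Together they serve the second bullet of the protocol's Objectives.

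**2. What is open when the blind is removed.**

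| Choice | Fixed in the SAP | Left open |
|---|---|---|
| Implausible registry counts (7.5) | Verify or correct the value; report decisions | What counts as implausible; what to do if it cannot be verified |
| Missingness judgement (7.5) | For the primary outcome: 5% threshold, Little's test, then MICE or complete cases | The judgement for each secondary outcome |
| Missing collection periods (7.5, 8.1) | MICE by period, then summed as a passive variable | The imputation model for the periods |
| Nonconvergence (9.1, 9.2) | Nothing beyond dealing with it when it occurs | The remedy |
| Length-of-stay sensitivity analyses (9.2.1) | Similar to 9.1.1 | The exact form |
| Adherence levels (9.1.1) | Ward-level factor with k + 1 levels | k and the cut-points, although these arise first for the primary outcome |

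The first five rows can still be open for a secondary outcome when the blind comes off. The last is a ward-level quantity shared by all outcomes, so it would normally be settled during the primary analysis.

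**3. Whether these decisions need the arms.** Cleaning, the missingness judgement, the imputation models and the basic two-arm comparison can all be done with arms coded A and B. The adherence model in 9.1 and the restricted sample in 9.1.1 differ. Adherence runs from 0 to 1 towards NOST and is expected to be almost collinear with arm, and the exclusions are defined differently for NOST and control wards. Either would show which code is NOST.

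**4. What the code is worth after the primary result.** Inputs from SAP section 6: risks 0.40 and 0.60, ICC 0.10, 30 observations per ward, 26 wards per arm.
- Design effect: 1 + (30 − 1) × 0.10 = 3.9.
- Standard error of the difference: √[(0.40 × 0.60 + 0.60 × 0.40) × 3.9 / (30 × 26)] = √(0.48 × 3.9 / 780) = 0.049.
- Planned difference over standard error: 0.20 / 0.049 = 4.1.

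If the planned effect is real, the estimate has the correct sign with probability above 0.99. The team could then probably identify the NOST arm from the coded primary result. Decisions made after that result gain little from the code, so what matters is that they are recorded before it.

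**The case against.** Much of the case on the other side stands.

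**The limit is disclosed.** A reader might infer that the SAP contradicts itself or claims protection the secondary outcomes do not have. The text does not support that. SAP 4.4 states the limit one paragraph after the general statement. Only the design table in 4.1 lacks the qualifier.

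**A purpose may exist.** A reader might infer that unblinding at this point serves nothing. The documents show only that no reason is given. The adherence model and the 9.1.1 exclusions do depend on knowing which arm is NOST.

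**Freedom is already limited.** Analyses follow lock, so unblinding cannot alter how outcomes were ascertained. Estimands, effect measures and estimators are set for each outcome, and code is tested beforehand. If more than 5% of wards lack primary data and the data are judged missing at random, the imputation model in 7.5 includes the secondary outcomes, so these must be prepared at the blinded stage. This narrows the open choices but does not remove those in the first five rows of the table. Code tested on fictitious data cannot settle points deferred to the real data.

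**No error rate can be attached.** A reader might want to express the harm as an inflated false-positive rate. Suppose (assumption, not in the documents) that an analyst picks the most NOST-favourable of 2, 3 or 4 processing options whose z statistics correlate 0.95, 0.9 or 0.8. The chance of a false result favouring NOST is then about 3.2%, 4.2% or 5.7%, against a nominal 2.5%. But an analyst who sees only A and B and picks the largest absolute z gives the same three rates. The inflation comes from choosing among options, and coded arms alone do not prevent that. These figures therefore do not measure the effect of unblinding.

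**The code is weak.** As shown above, a large primary effect or the adherence data may reveal the arms. This limits what a longer blind achieves and moves the remedy towards archiving decisions early.

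**Conclusion.** The point holds as a modest one. By rule and without a stated reason, the SAP unblinds before 8 of its 9 outcomes are analysed, and for those outcomes some processing, missing-data, convergence and sensitivity choices are still to be made. The possible bias is limited by database lock, prespecified estimators and reporting of deviations. Its size is unknown, and it is nil if every choice happens to be fixed beforehand. The primary outcome is not affected.

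This rests on reading the SAP's undefined term for the secondary analyses as including the eight secondary outcomes, which is the natural reading.

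**What to change.** Replace the end of SAP 4.4 with wording such as:

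> Decisions on data cleaning, missing data and imputation (including missing collection periods), handling of nonconvergence, and adherence categories will be made for all nine outcomes with arms coded, and archived with a date. This will be done before the primary result is seen, before the adherence model or the exclusions in 9.1.1 are run, and before the blind is removed. The simple randomised comparison of each secondary outcome will also be run on coded arms where feasible. The blind will then be removed.

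Two smaller edits go with it:
- Qualify the Blinding row in SAP 4.1 so that it matches what 4.4 provides.
- State the length-of-stay sensitivity analyses in 9.2.1 in full.

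If the sponsor has a reason to unblind before the secondary outcomes, 4.4 should give it; archiving the decisions beforehand remains worthwhile.

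The cost is SAP wording, some decisions taken earlier than planned, and a slightly later unblinding. No new data or staff are needed.
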